### **7.3 Methods and Timing of Assessing, Recording, and Analysing Efficacy Data**

Methods for assessing efficacy data are listed below and are described in further detail in the IRC. Timing of efficacy assessments are discussed in Section 5. Procedures for recording efficacy data are discussed in Section 14.1, and methods of analyses are discussed in Section 10.4.5.

All images will be sent to a central ICL for QC and central read management. This comprises the following images:

- Priorsstr2 agonist positive PET scans (see Section 4.1)
- All  $^{68}\text{Ga}$ -OPS202 PET/CT scans.

The details of imaging set management and read design will be fully described in the IRC. This will include the following:

- Full acquisition guidelines for the site
- Process for PET scanner quality control (phantom assessments and reporting)
- Image transmission methodology

- Core lab QC methodology and management of the images
- Read design for primary endpoint
- Read design for secondary endpoint and process for calculating tumour-to-background ratio and  $SUV_{max}$
- Design of exploratory endpoints
- Conduct of the read
- Management, training and inter-reader evaluation
- Data management
- Data export overview
- Archiving of images.

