1.3.2 Subjects assessments

1.3.2.1 Efficacy assessments

The sets of images obtained at Visit 2 and Visit 3 for the primary endpoint and most of the secondary endpoint analyses will be sent to an ICL for centralised blinded reading by two independent experienced radiologists/nuclear medicine physicians, and a third for adjudication of discordances if required. The readers will be specifically trained for this protocol.

All the images will be reviewed according to the workflow illustrated in the [Figure 2](#) below.

Figure 2 Flow Chart of the Independent Review Methodology

Full details of the read design and conduct is provided in the Independent Review Charter (IRC).

For the primary endpoint analysis, the number of lesions on each subject scan will be counted on a per organ basis by the two primary independent readers. The independent readers will be blinded to subject, site, peptide mass dose, radioactivity dose, and the temporal sequence of dosing. In case of discrepancy, images will go to the adjudicator (third reader) for a final read and adjudication.

After blinded reading, the readers will compare the paired scan for each subject and note which of the pair provides superior images based on overall image quality and lesion count.

The primary endpoint is the mean number of lesions identified in each tabular cell (see [Table 1](#)) as a ratio of the maximum number of lesions identified per organ per subject, removing individually differing absolute lesion numbers as a confounder and allowing the factorial design to be established to identify the optimum peptide mass and radioactivity dose.

Details for computation and analysis of primary efficacy criterion are provided in section 3.2.1.1.

The sequence of image display and recording of results will be as follows on a per subject basis:

- (1) Review of the two image sets of ^{68}Ga -OPS202 scans in randomised step-wise fashion, without and with CT image fusion. The PET and CT images acquired at the same time will be used for co-registration
- (2) CT images for standard-of-truth (SOT) assessments will be reviewed by two radiologists not involved in PET/CT images read. It is not anticipated that there will be a difference in the lesion counts between the two visits related to disease progression, due to slow development of GEP-NETs; however, there may be technical reasons for variations between the scans

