3.1.1 Primary efficacy endpoint(s)

For each combination of injected peptide/radioactivity dose range, differences in relative lesion counts derived from a 2×3 factorial analysis measuring the ratio of the number of lesions detected by ⁶⁸Ga-OPS202 to the number of lesions assessed by SOT (descriptive analyses).

The SOT in this study is the CT scan images acquired at Visit 2 and Visit 3.

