3.2.1.1 Primary efficacy analysis

The primary endpoint is the relative lesion count, measuring the ratio of the number of lesions detected by ⁶⁸Ga-OPS202 to the number of lesions assessed by SOT.

The SOT is the CT scan images acquired at Visit 2 and Visit 3, using number of lesions identified by the reader on both timepoints together (provided by ICL), in order to take into account potential variability within subject or partial volume effect.

For each PET/CT assessment, this ratio will be computed, as indicated below:

$$\text{Relative lesion count} = \frac{\text{Number of lesions detected by } 68\text{Ga} - \text{OPS202}}{\text{Number of lesions detected by SOT}}$$

Numerator and denominator will be available in the database provided by ICL.

Selection of the optimal dose range for peptide mass and radioactivity of ⁶⁸Ga-OPS202 will be based on the observed highest relative lesion counts, based on provided descriptive statistics: n (number of non-missing observations), number of missing values (if any), arithmetic mean, standard deviation (SD), median and the range (minimum, maximum). Those descriptive statistics will be used for analysing all continuous parameters.

Analysis over all organs

For each PET/CT and PET assessment, relative lesion count will be computed over all lesions of all organs.

The denominator, based on SOT, will be computed over all organs.

Analysis per organ

For each PET/CT and PET assessment, relative lesion count will be computed for each of the following organs:

- Primary site of GEP-NET (among all subjects with at least one lesion detected by SOT on primary site of GEP-NET).
- Lymph nodes (among all subjects with at least one lesion detected by SOT on lymph nodes).
- Liver (among all assessed subjects with at least one lesion detected by SOT on liver).

- Axial/appendicular skeleton (bones) (among all assessed subjects with at least one lesion detected by SOT in bones).
- Lungs (among all assessed subjects with at least one lesion detected by SOT in lungs).

The denominator, based on SOT, will be computed for each organ.

Relative lesion count (over all organs then per organ) will be summarised using descriptive statistics for:

- each of the six combinations of injected peptide/radioactivity dose range, presented in such a way that study arms are explicit
- each of the two peptide mass dose ranges
- each of the three radioactivity dose ranges

No statistical test will be performed (no p-value nor confidence interval).

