- Scatterplot of radioactivity dose/kg x SUV_{max}, per each of the four organs
- Scatterplot of radioactivity dose/kg x absolute number of lesions detected by ⁶⁸Ga-OPS202, per each of the five anatomic sites (Primary site of GEP-NET, Lymph nodes, Liver, Axial/appendicular skeleton (Bones), Lungs).
- Scatterplot of radioactivity dose/kg x difference between number of lesions detected by ⁶⁸Ga-OPS202 and number of lesion detected by SOT, per each of the five anatomic sites.

Besides, as categorical analysis of the radioactivity dose/kg, the following ranges will be used for the analysis, based on the observed distribution of the continuous radioactivity dose/kg among PP population:

- [min-Q1] MBq/kg
-]Q1-median] MBq/kg
-]median-Q3] MBq/kg
-]Q3-max] MBq/kg

Based on those ranges, summary tables with descriptive statistics for each of the four ranges of radioactivity dose/kg will be provided. Also, into each of the four ranges of radioactivity dose/kg, the two peptide doses will be analysed, that will lead to analyse, with same methodology as previously, 8 combinations of radioactivity dose/kg x peptide mass dose ranges.

Listings of individual values will be provided by ascending radioactivity dose/kg range then by ascending radioactivity dose/kg, and by subject (and by organ when applicable).

Exploratory efficacy endpoints:

- e) Preliminary diagnostic sensitivity of ⁶⁸Ga-OPS202 imaging of GEP-NETs by both subject-based and lesion-based analysis compared to standard-of-truth; and organ-based specificity, by radioactivity dose range (i.e. 40-80 MBq, 100-140 MBq, 160-200 MBq, 100-200 MBq, 40-200 MBq).

Diagnostic sensitivity between ⁶⁸Ga-OPS202 and SOT will be assessed using performance specified in table below.

Table 3 Diagnostic performance of ⁶⁸Ga-OPS202 compared to SOT

⁶⁸ Ga-OPS202 PET/CT scan results	SOT results	
	# of lesions detected	# of lesions not detected
# of lesions detected	True Positive (TP)	False Positive (FP)
# of lesions not detected	False Negative (FN)	True Negative (TN)

The sensitivity corresponds to the probability that the ⁶⁸Ga-OPS202 imaging detects the lesions, given that the lesions are positive in SOT.

For each PET/CT assessment, the sensitivity will be computed using following formula, per each of the organs (lesion-based approach) and overall (subject-based approach):

$$Sensitivity = \frac{TP}{TP + FN}$$

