f) Comparison to sstr2 agonist positive scan results will be computed for sensitivity analysis. In order to compare ^{68}Ga -OPS202 PET/CT to sstr2 agonist PET assessments, the two following analyses will be performed:

- Sensitivity and specificity of previously acquired sstr2 agonist PET versus SOT. Diagnostic sensitivity of previously acquired sstr2 agonist scan (at Visit 1) will be analysed by subject-based analysis and lesion-based approaches (per organ) compared to SOT.

Also, organ-based specificity will be computed.

Methodology for computing sensitivities and specificity will be same as described in e), with sstr2 PET instead of ^{68}Ga -OPS202 PET/CT assessments, compared to SOT.

As sstr2 agonist PET scan is performed only at Visit 1 and as SOT is not specific to V2 or V3, values of sensitivities/specificity will be unique per subject.

Subject-based and lesion-based sensitivity along with organ-based specificity will be summarised using descriptive statistics for all subjects.

Individual values of subject-based, lesion-based sensitivity and organ-based specificity will be listed by subject for this assessment (sstr2 PET).

- Comparison of sensitivity of ^{68}Ga -OPS202 PET/CT to previously acquired SSTR2 agonist PET.

The subject-based sensitivity of ^{68}Ga -OPS202 PET/CT will be compared to sensitivity of previously acquired SSTR2 agonist PET, both assessed vs SOT.

Therefore for each subject*visit, the difference will be computed as:

Sensitivity (PET/CT vs SOT) – Sensitivity (SSTR2 vs SOT).

Note that value of subject-based sensitivity (SSTR2 vs SOT) will be unique per subject.

This difference will be summarised using descriptive statistics for:

- each of the six combinations of injected peptide/radioactivity dose range
- each of the two peptide mass dose ranges
- each of the three radioactivity dose ranges

It will be also summarised using descriptive statistics for following five radioactivity dose groups:

- Difference of ^{68}Ga -OPS202 PET/CT (at 40 to 80 MBq) to SSTR2 PET
- Difference of ^{68}Ga -OPS202 PET/CT (at 100 to 140 MBq) to SSTR2 PET
- Difference of ^{68}Ga -OPS202 PET/CT (at 160 to 200 MBq) to SSTR2 PET
- Difference of ^{68}Ga -OPS202 PET/CT (at 100 to 200 MBq) to SSTR2 PET
- Difference of ^{68}Ga -OPS202 PET/CT (at 40 to 200 MBq) to SSTR2 PET

g) SUV_{max} ratio for lesions

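### SAP 3.2.1.2 f): the OPS202-minus-agonist sensitivity difference contains a CT-fusion component that can only favour OPS202, because only the OPS202 read is fused with the CT that supplies the standard of truth

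*SAP*

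**What the plan says.** **Standard of truth.** SAP 3.2.1.1: "The SOT is the CT scan images acquired at Visit 2 and Visit 3", with lesions identified on both timepoints together. Section 3.1.1 and protocol section 3.2.1 define it in the same way.

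**OPS202 read.** SAP 1.3.2.1 has the two OPS202 image sets reviewed "without and with CT image fusion. The PET and CT images acquired at the same time will be used for co-registration". Two reads therefore exist per scan, and the fused one uses the CT of that visit. For sensitivity only the fused read is used. SAP 3.2.1.2 e): "For each PET/CT assessment, the sensitivity will be computed using following formula". Lesions are counted from the core lab's Lesion Matching Table.

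**Agonist read.** SAP 3.2.1.2 f): "Methodology for computing sensitivities and specificity will be same as described in e), with sstr2 PET instead of" OPS202 PET/CT, against the same SOT, giving one value per subject. Protocol section 7.3 likewise lists the prior images as "agonist positive PET scans (see Section 4.1") and the OPS202 images as PET/CT scans.

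**Contrast.** For each subject and visit: "Sensitivity (PET/CT vs SOT) – Sensitivity (SSTR2 vs SOT"). It is summarised descriptively by dose combination, by peptide range and by radioactivity group.

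**What is not planned.** OPS202 PET-alone counts are used for the relative lesion count (3.2.1.1) and the absolute number of lesions (3.2.1.2 c), but no PET-alone sensitivity is computed. Neither item f) nor SAP section 5 mentions that the two sides of the subtraction rest on different kinds of read.

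**The concern.** A comparison of two tracers should change the tracer and hold the rest of the reading conditions fixed. Here a second factor changes too. The OPS202 readers have in view the CT from which the reference lesions are counted, and the agonist is scored as PET. A lesion that is faint on PET but plain on CT has a second route to being counted as an OPS202 true positive, and on the plan's wording it has no such route for the agonist.

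The result bears on the product's rationale. Protocol section 2.1 puts forward better diagnostic performance than sstr2 agonists as the promise of OPS202, and item f) is where the plan compares sensitivity with an agonist. The opening of SAP 3.2.1.2 also lets the exploratory endpoints inform selection of the optimal dose range. A positive difference in f) would naturally be read as a tracer advantage, although part of it could come from the CT.

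**Working it through.** The plan states no expected sensitivity, power or sample size for this comparison, so there is no figure to reproduce. The check sets out the structure of the contrast and then sizes the fusion term under stated assumptions.

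**1. The two sides of the subtraction**

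| | OPS202 | Agonist |
|---|---|---|
| Read used | PET/CT (SAP 3.2.1.2 e) | PET (SAP 3.2.1.2 f) |
| CT available to the reader | same-visit CT, part of the SOT (SAP 1.3.2.1) | none mentioned |
| Reference | Visit 2 and 3 CT | Visit 2 and 3 CT |
| Timing relative to the SOT | concurrent | up to 6 months before screening (protocol 4.1) |

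**2. Fusion term.** Assume both tracers have the same PET-alone sensitivity s against the SOT, so the true tracer difference is 0. Assume fusion recovers a fraction f of the SOT lesions missed on PET alone, with no correct call withdrawn.

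- OPS202 PET/CT sensitivity = s + f(1-s)
- Agonist PET sensitivity = s
- Planned difference = f(1-s), which is never negative

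Both s and f are assumptions. Over a range:

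| s | f = 0.10 | f = 0.25 | f = 0.50 |
|---|---|---|---|
| 0.5 | +0.050 | +0.125 | +0.250 |
| 0.6 | +0.040 | +0.100 | +0.200 |
| 0.7 | +0.030 | +0.075 | +0.150 |
| 0.8 | +0.020 | +0.050 | +0.100 |
| 0.9 | +0.010 | +0.025 | +0.050 |

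For example, at s = 0.7 and f = 0.25: 0.25 × 0.30 = 0.075.

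**3. Entry selection, which works the other way.** Protocol 4.1 requires a positive receptor scan, and 4.2 sets a lower limit of five lesions on it. Protocol 7.3 refers back to 4.1 for the agonist images, so this is the comparator scan. Subjects whose agonist scan happened to detect many lesions are more likely to enter, which raises observed agonist sensitivity. A binomial simulation (400,000 subjects per scenario before selection, equal tracers, at least five agonist-detected lesions to enter, SOT lesions per subject assumed uniform) gave:

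| Lesions per subject | s | f = 0 | f = 0.10 | f = 0.25 | f = 0.50 |
|---|---|---|---|---|---|
| 5 to 15 | 0.5 | -0.077 | -0.027 | +0.048 | +0.173 |
| 5 to 15 | 0.7 | -0.034 | -0.003 | +0.041 | +0.116 |
| 5 to 15 | 0.9 | -0.010 | +0.001 | +0.016 | +0.041 |
| 5 to 30 | 0.5 | -0.024 | +0.026 | +0.101 | +0.226 |
| 5 to 30 | 0.7 | -0.013 | +0.017 | +0.062 | +0.137 |
| 5 to 30 | 0.9 | -0.004 | +0.007 | +0.021 | +0.046 |

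Selection alone (f = 0) shifts the difference by -0.004 to -0.077. The two effects add: at s = 0.7, f = 0.25 and 5 to 15 lesions, 0.075 - 0.034 = 0.041. With f = 0.10 and 5 to 15 lesions the net is about zero or slightly negative. The upper limit of 25 lesions per organ and the age of the scan were not modelled.

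**4. The like-for-like contrast.** OPS202 PET minus agonist PET is s - s = 0 for equal tracers before selection, so the fusion term is gone. The selection shift stays. The gap between the planned contrast and the like-for-like one is OPS202 PET/CT minus OPS202 PET sensitivity, which is f(1-s) in this model. Reporting both contrasts therefore shows the fusion effect directly.

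**The case against.** **The SOT is read by other people.** SAP 1.3.2.1 assigns it to two radiologists not involved in the PET/CT read. It also uses both timepoints together, whereas each fused read has one visit's CT. Both facts limit the overlap. Neither removes it, since separate readers still look at shared images.

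**The reading rules are not in hand.** What counts as detected by OPS202 is left to the Imaging Review Charter, which is not among the documents. The CT is described as serving co-registration. The SAP calls the agonist assessment PET but does not say that CT was withheld from it. This stands as a limit on what can be said about f. If the agonist scan were read with a CT of its own date, that would still not be the Visit 2 or 3 CT.

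**PET/CT is the intended use.** The exploratory objective concerns the sensitivity of PET/CT imaging. That is a good reason to keep the planned difference, but not to let it stand as the only tracer comparison.

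**The stakes are modest.** Item f) is exploratory and untested, and the single agonist value per subject cancels when two doses are compared within a subject. This stands: the point concerns the tracer comparison, not the ranking of doses.

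**Stronger readings that the documents do not support.** A reader might infer that the whole difference is biased towards OPS202. Entry selection pushes the other way, and the older agonist scan adds a time gap whose effect the documents do not settle. A reader might also picture 7 of 10 lesions rising to 9 of 10 with fusion, a 20-point gain. That needs f = 2/3, beyond the range used here, and nothing in the documents supports it. Finally, a reader might conclude that the PET-alone count should drive dose selection for the primary endpoint. SAP 3.2.1.1 introduces that ratio for the PET/CT assessment and already reports PET-alone counts by dose, so which read leads is a matter of judgement.

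**Conclusion.** The point holds for item f). The planned difference sets an OPS202 read fused with the reference CT against an agonist read described as PET, so it cannot separate the tracer from the fusion. The fusion component favours OPS202. With equal tracers it is f(1-s), or +0.01 to +0.25 over the assumed ranges.

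This rests on three assumptions: s and f, which the documents do not give; fusion adding SOT lesions to the OPS202 count without removing any; and the agonist being read without the SOT CT, as the wording of SAP 3.2.1.2 f) and protocol 7.3 indicates. The sign of the net bias is open, since under some of the assumptions tried, entry selection cancels or slightly outweighs the fusion term. An opposing bias of unknown size does not justify keeping one that can be avoided.

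**What to change.** In SAP 3.2.1.2 f):

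1. Compute OPS202 PET-alone sensitivity against the SOT with the formula in e).
2. Report OPS202 PET minus agonist PET, both against the SOT, as the like-for-like tracer comparison, with the same summaries as now planned.
3. Keep OPS202 PET/CT minus agonist PET alongside it.
4. State as limitations that the fused read shares its CT with the SOT, that entry depended on the receptor scan, and that this scan may be months older than the SOT CT.

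No change to the primary endpoint is proposed.

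The cost is more than SAP wording if the core lab has matched only the fused read. Sensitivity needs lesion-level matches, not counts, so the Lesion Matching Table must cover the PET-alone read. That read already exists, and items a) and b) already restrict PET measurements to SOT-confirmed lesions for up to five lesions per organ, so part of the matching may be available. The PET-alone result is also further from clinical use, which is why the PET/CT difference stays.

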**Figure 1 Study Design and Subjects Allocation**

Subject participation in the study is estimated to last approximately 7 weeks and will include:

- Visit 1: A screening period up to 2 weeks
- Visit 2: A single intravenous (i.v.) injection of the first peptide/radioactivity dose of  $^{68}\text{Ga}$ -OPS202 on Day 1 followed by PET/CT scan imaging 1 hour post dosing (up to 80 min)
- Visit 3: A single i.v. injection of the second peptide/radioactivity dose of  $^{68}\text{Ga}$ -OPS202 followed by PET/CT scan imaging 1 hour post dosing (up to 80 min). This visit is scheduled 15 to 21 days after the first  $^{68}\text{Ga}$ -OPS202 administration (Visit 2)
- Visit 4: A 2-week follow-up period for evaluation of safety.

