[16] **Adverse events:** Subjects must be followed for AEs, regardless of relationship, from the time they signed the informed consent until at least 14 days after the last dose of investigational imaging product (IIP). Clinically significant changes in physical examination, vital signs, electrocardiogram and laboratory findings will be recorded as an adverse event

[17] **Compliance:** The dose injected will be recorded at each visit.

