## 6 DIAGNOSTIC IMAGING OF SUBJECTS

### 6.1 Study Imaging Product

#### 6.1.1 Ga-OPS202

At Screening, subjects will be allocated a subject number. Following confirmation of eligibility for the study, subjects will be randomised to one of the following sequence of Ga-OPS202 peptide mass dose/ radioactivity dose ranges:

- Arm A: 5-20 µg/ 40-80 MBq at Visit 2 and 30-45 µg/ 100-140 MBq at Visit 3

or

- Arm B: 5-20 µg/ 100-140 MBq at Visit 2 and 30-45 µg/ 160-200 MBq at Visit 3

or

- Arm C: 5-20 µg/ 160-200 MBq at Visit 2 and 30-45 µg/ 40-80 MBq at Visit 3

Ga-OPS202 is a diagnostic medicinal product with three main components, namely:

- Ga, a positron emitter radionuclide with a half-life of 68 min
- NODAGA, a chemical chelator group, and
- JR11, an antagonist somatostatin analogue that binds to sst2 receptors

OPS202 (cold kit) is available for clinical trials in a 50 µg peptide dose vial, and is radiolabeled using a Ge/Ga-generator. Due to the short half-life (68 min) of the Ga radioisotope, on-site generation of Ga-labeled radiopharmaceuticals is mandatory. The Ga is eluted initially from the generator with hydrochloric acid and the eluate combined with the reconstituted peptide kit preparation. The radiolabelling occurs at room temperature. The product then undergoes radiopharmaceutical quality control (see Preparation, Radiolabeling and QC manual).

The radiolabelled OPS202 (Ga-OPS202) consists of 50 µg of peptide in a total volume of 6 mL (8.33 µg/mL). Sampling of 0.5 mL for QC yields 5.5 mL solution from which the volume to be administered is withdrawn. This volume to be injected is calculated to obtain the target peptide mass dose and the desired radioactivity dose.

The calculation of the volume takes into account the different components that determine the final radioactivity dose, the subject will be exposed to, in particular:

- The amount of Ga eluted from the generator which depends on the latter half-life
- The time elapsed between OPS202 (cold kit) radiolabelling and the injection of Ga-OPS202 to the subject (decay of Ga), the variation of which is a tool to adjust the final peptide/radioactivity dose required to be injected
- The required peptide mass dose and radioactivity dose of Ga-OPS202 to be injected.

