For each PET assessment, lesion SUV_{max} will be measured for each of the most avid lesions identified per organ (up to a maximum of five most avid lesions per organ that are confirmed by SOT) and reported in the ICL database.

For each organ, the SUV_{max} ratio will be computed as follows:

$$SUV_{max} \text{ ratio} = \frac{SUV_{max}}{SUV_{mean} \text{ of the subject's reference tissue (tumour – free liver)}}.$$

It will be analysed using descriptive statistics, presented for:

- each of the six combinations of injected peptide/radioactivity dose range
- each of the two peptide mass dose ranges
- each of the three radioactivity dose ranges

Individual values of SUV_{max} ratio will be listed by subject, by organ and by visit.

Background location will be specified (L: Liver, B = Aortic blood).

h) SNR in the liver

SNR will be calculated from lesion-free VOI (reference tissue) using following formula:

$$SNR = \frac{SUV_{mean}}{SUV_{SD}}$$

Those SUV_{mean} and SUV_{SD} will be available in the database provided by ICL.

A higher SNR in the liver indicates higher effectiveness of ^{68}Ga -OPS202 as a diagnostic agent.

It will be analysed using descriptive statistics, presented for:

- each of the six combinations of injected peptide/radioactivity dose range
- each of the two peptide mass dose ranges
- each of the three radioactivity dose ranges

Individual values of SNR in the liver will be listed by subject and by visit.

Background location will be specified (L: Liver, B = Aortic blood).

Additional listing:

A listing of SUV measurements by lesion and per organ will be provided, including following data listed by subject and by visit:

- Lesion SUV_{mean}
- Lesion SUV_{max}
- Lesion SUV_{max} ratio
- Lesion Tumour-to-background ratio

3.2.2 *Safety*

All safety data will be included in the data listings and summary tables will be based on the Safety population and presented by combination of injected peptide/radioactivity dose range and overall.

AEs will be allocated to each combination of injected peptide/radioactivity dose range following the following rule: AEs will be allocated to the last dose of ^{68}Ga -OPS202 received, based on AE start date/time.

Same rule will be applied for analysing concomitant medications, based on treatment start date/time.

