3.2.2.1 Adverse events

All AEs will be recorded and graded by investigators using the NCI CTCAE classification (Version 4.03, dated 14 June 2010), will be coded using the MedDRA Version 19.1 or higher, and will be classified by MedDRA PT and SOC.

Listings will be presented and sorted by combination of injected peptide/radioactivity dose range of ⁶⁸Ga-OPS202, subject number, start date of AEs, primary SOC, PT and verbatim text for all adverse events recorded during the study.

Listings of SAEs, AEs leading to IIP withdrawal and AEs leading to death (fatal outcome) will also be presented.

Also, a listing of grade ≥ 3 AEs will be provided.

Treatment Emergent Adverse Events (TEAEs) will be flagged (*) in the AE listings and will be summarised.

A TEAE is defined as any AE that occurs during the study if:

- (1) it was not present prior to receiving the first ⁶⁸Ga-OPS202 injection, or
- (2) it was present prior to receiving the first ⁶⁸Ga-OPS202 injection but the intensity increased during the study, or
- (3) it was present prior to receiving the first ⁶⁸Ga-OPS202 injection, the intensity is the same but the causality became related during the study.
- (4) AEs starting > 28 days after last ⁶⁸Ga-OPS202 injection will not be considered as TEAEs.

An overall summary table of all AEs will be presented by combination of injected peptide/radioactivity dose range and overall.

TEAEs will be summarised by combination of injected peptide/radioactivity dose range and overall with the number and percentage of subjects with adverse events classified by primary SOC and PT. The number of occurrences of a TEAE will also be presented.

In addition, summary tables will also be presented for SAEs, TEAEs by intensity and causality and TEAEs associated with withdrawals.

In the event of multiple occurrences of the same AE (same PT) being reported by the same subject, the maximum intensity (Grade 5 > Grade 4 > Grade 3 > Grade 2 > Grade 1 > missing > not applicable) and the most serious causality (related > missing > not related) will be chosen. Nonetheless, for the table “Overall summary of adverse events”, in the cross classification of causality and intensity, any subject experiencing multiple AEs with different intensities for each causality category will be counted for each intensity.

3.2.2.2 *Laboratory data*

A separate listing of normal ranges for Standard International (SI) units will be provided by gender and age where relevant.

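### By-combination AE tables give low-peptide cells 15 to 21 planned days at risk and high-peptide cells about 14, with no common window

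*SAP*

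**What the plan says.** SAP 3.2.2 (Safety) bases its summary tables on the safety population, "presented by combination of injected peptide/radioactivity dose range and overall". Its allocation rule is that "AEs will be allocated to the last dose of" 68Ga-OPS202 received, judged by the AE's start date and time. SAP 3.2.2.1 then reports treatment-emergent AEs as counts and percentages of subjects, plus numbers of occurrences. The only time limit is that "AEs starting > 28 days after last" 68Ga-OPS202 injection are not treatment-emergent.

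Protocol 6.1.1 fixes the order of the peptide ranges:

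- "Arm A: 5-20 µg/ 40-80 MBq at Visit 2 and 30-45 µg/ 100-140 MBq at Visit 3"
- "Arm B: 5-20 µg/ 100-140 MBq at Visit 2 and 30-45 µg/ 160-200 MBq at Visit 3"
- "Arm C: 5-20 µg/ 160-200 MBq at Visit 2 and 30-45 µg/ 40-80 MBq at Visit 3"

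Protocol 3.1 says of Visit 3: "This visit is scheduled 15 to 21 days after the first" administration. Visit 4 follows two weeks after the second scan. Footnote 16 to Protocol Table 5 requires AE follow-up "until at least 14 days after the last dose of investigational imaging product (IIP").

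Protocol 10.4.7 plans AE incidence by dosing arm and overall. SAP section 5, which lists departures from the protocol, does not mention the move to tables by combination.

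**The concern.** The last-dose rule makes the window for the first dose equal to the gap between injections, and the window for the second equal to the follow-up after Visit 3. Because the low peptide range always comes first, the difference in window length falls wholly on the peptide comparison and, as planned, always in one direction. Randomisation to arm cannot average it out.

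A percentage of subjects with an AE rises with observation time for any event that accrues at a background rate. A reader who compares peptide ranges in the planned table would then see part of the difference in days as a difference in safety. What is at stake is how one descriptive table reads.

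**Working it through.** **Inputs.** Gap from first to second injection: 15 to 21 days (Protocol 3.1). Second injection to Visit 4: 14 days (Protocol 3.1 and 5.2.4). Minimum AE follow-up after the last dose: 14 days (Protocol Table 5, footnote 16). Treatment-emergent limit: 28 days after the last injection (SAP 3.2.2.1). Planned cell size: 8 (SAP Table 1). The documents give no AE risk for this trial, so the 14-day risk p14 is an assumption, shown over a range.

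**1. The plan's own calendar.** Visit 3 = Day 1 + 15 to 21 = Day 16 to 22. Visit 4 = Visit 3 + 14 = Day 30 to 36. Both match Protocol Table 5, so the windows are read as intended.

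**2. Time at risk.** The window runs from an injection to the next injection, or to Visit 4.

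- Low peptide: 15 to 21 days, or 8 × 15 = 120 to 8 × 21 = 168 person-days per cell.
- High peptide: 14 days, or 8 × 14 = 112 person-days per cell.
- Ratio: 15/14 = 1.07; 18/14 = 1.29; 21/14 = 1.50.

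The 28-day limit exceeds both 21 and 14 days, so it shortens neither window.

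**3. Effect on the percentage of subjects with an AE.** With the same constant hazard in both windows, p(t) = 1 − (1 − p14)^(t/14). For p14 = 20%: 1 − 0.8^(15/14) = 21.3% and 1 − 0.8^(21/14) = 28.4%.

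| Assumed p14 (high-peptide cell) | Low, 15 d | Low, 18 d | Low, 21 d | Excess per cell of 8 (15 to 21 d) |
|---|---|---|---|---|
| 10% | 10.7% | 12.7% | 14.6% | 0.1 to 0.4 |
| 20% | 21.3% | 24.9% | 28.4% | 0.1 to 0.7 |
| 30% | 31.8% | 36.8% | 41.4% | 0.1 to 0.9 |
| 50% | 52.4% | 59.0% | 64.6% | 0.2 to 1.2 |

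At 20% a cell of 8 expects 8 × 0.20 = 1.6 subjects with an AE in the high-peptide window, against 8 × 0.213 = 1.7 to 8 × 0.284 = 2.3 in the low-peptide window. Over all 24 subjects the excess is 5.1 − 4.8 = 0.3 to 6.8 − 4.8 = 2.0.

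**4. What is not tilted.**

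- By arm: planned follow-up from the first injection is 15 + 14 = 29 to 21 + 14 = 35 days in every arm.
- Pooled radioactivity ranges: each has one Visit 2 cell and one Visit 3 cell, so 120 + 112 = 232 to 168 + 112 = 280 person-days in each range.
- Events within hours or days of injection fall inside both windows.

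**5. With a 14-day window after each injection.** 14 against 14 days, 112 against 112 person-days per cell, ratio 1.00. Each low-peptide window loses 1 to 7 days.

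**The case against.** A reader might infer that safety by combination is a secondary objective, and that this tilt therefore damages one. The documents do not support that. The objective in Protocol 2.2 and SAP 1.1.2 is to describe safety and tolerability in the population. The endpoints in Protocol 3.2.3 contain no dose contrast, and the overall column that answers them is unaffected.

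A reader might also infer that the tilt could mislead the choice of dose. SAP 3.2.1.1 and 3.2.1.2 rest that choice on relative lesion counts and the other efficacy endpoints, not on AE percentages. No safety test is planned, so no error rate is involved.

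Nor can it be said outright that low-peptide cells will show more AEs, or that a real increase at the higher mass would be hidden. That needs background or late events. Protocol 1.4 cites guidance that less than 50 µg of peptide is not expected to have a clinically significant pharmacological effect, the radionuclide half-life is 68 minutes, and SAP 3.2.2.1 also tabulates by causality. On the other side, Protocol 1.1 reports AEs in 6 of 12 subjects of the earlier study, most judged unlikely or not related, so background events do occur.

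Further limits stand:

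- A ratio of 1.50 needs every subject to return on the last permitted day.
- Fourteen days is a minimum. If events were captured up to 28 days after the second dose, the tilt would reverse (28/21 = 1.33 to 28/15 = 1.87). Protocol 8.1.3 asks for reports after completion only where a causal link is suspected, so this is not the planned case.
- Under Protocol 5.2.4.1 a subject withdrawn after the first dose is evaluated at about two weeks, so not every low-peptide window is longer.
- SAP Appendices 1 and 2 were not available. A window defined there cannot be excluded.

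Keeping every AE under the last dose is a defensible descriptive summary. These points reduce the consequence; they do not remove the unequal windows.

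**Conclusion.** The point holds as a minor one. As planned, low-peptide cells have 7% to 50% more time at risk than high-peptide cells, and nothing in the SAP text equalises this. The imbalance arises from the SAP's allocation rule: the protocol's by-arm tables would have equal planned follow-up.

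The effect is confined to background or late-onset AEs in comparisons of peptide range within the by-combination table. At an assumed 20% risk over 14 days it is under one subject per cell of 8. That size rests on a constant hazard, on visits kept as scheduled and on AE collection ending at Visit 4. The direction also depends on the last of these.

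**What to change.** Add to SAP 3.2.2.1 a by-combination table of treatment-emergent AEs that start within 14 days of each injection, and name it as the table for any comparison between combinations. Keep the planned full-allocation table and the listings beside it. State how the 14 days are counted, and treat partial start dates as in SAP 3.2.3.2.

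Add a note that peptide range remains completely confounded with visit order, and that late events from the first dose may carry over into the second window. The common window cures neither. List the change from by-arm to by-combination AE tables in SAP section 5.

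The cost is one or two sentences, one derived flag and one table. SAP 3.2.3.2 already refers to days since last administration, so the timing variable appears to exist. The downside is that AEs starting on days 15 to 21 after the first dose are absent from the added table; they remain in the full-allocation and overall tables.
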